A blinded, 24-week trial of a hybrid DFI/CHW intervention among a population of low-income patients with poorly controlled diabetes. Participants would be randomized to one of three arms: 1) DFI intervention alone, 2) hybrid DFI/CHW intervention, 3) usual care. Participants assigned to the DFI alone arm would receive a free wireless glucometer if they dont already have one and be eligible for a lottery incentive if they use their glucometer. Participants assigned to the hybrid DFI/CHW intervention would receive the same glucometer if they dont already have one and lottery incentives. If, despite these strategies, they exhibited low adherence to self-monitoring or poor glucose control, they would also receive support from an IMPaCT CHW. The CHW support would incorporate two behavioral strategies which have been shown to help individuals cope with failure: positive affect induction and attribution retraining. Interventions: DFI Alone Arm: Participants will receive a free wireless glucometer if they dont already have one on the day of enrollment. To encourage habit formation, for the first 6 weeks of the trial, participants will be eligible for a daily lottery incentive for every day that they use their glucometer. We will use an approach similar to what we have used in prior DFI trials: the lottery will provide infrequent large payoffs (a 1 in 100 chance of a US\$50 reward) and more frequent small payoffs (an 18 in 100 chance of a US \$5 reward). The total average amount of financial incentives from these lotteries will be modest: an expected value of US\$1.40 per day. Participants who draw the winning lottery number, but did not check their glucose the day prior will receive an automated text or e-mail message informing them what earnings they would have won had they used their glucometer. After 6 weeks, we will terminate the lottery but continue to monitor patients adherence to glucose self-monitoring. A clinician at the practice site will receive notifications if participants glucose is either extremely low or high (60 or 400 mg/dL). Participants with these readings will receive messages to contact their healthcare provider immediately. Hybrid DFI/CHW Arm: Participants in the hybrid intervention will receive a wireless glucometer if they dont already have one and financial incentives just as in the DFI intervention. However, any individuals who have low adherence (no self-monitoring) or elevated glucose readings (300 mg/dL) for 30% of days over any 2 week period in the first 12 weeks of the study will be assigned to receive ongoing CHW support for the duration of the 24-week study period (Figure 3). Based on prior studies, we estimate that 50% (25 of the 50 patients in to the hybrid intervention) will require support from a CHW. Once a CHW receives notification of a struggling patient, she will visit the patient at home within 1-2 days to initiate the IMPaCT intervention.

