
the correct phone number using contact verification technology. Step Five: Labs 1. Walk the patient to the laboratory to have their blood drawn for HbA1c evaluation. 2. Provide the patient with a gift card and half page sheet with payment information Step Six: How to Use the Glucometer 1. Provide the patient with a glucometer if they don't already have one. 2. Review the user guide with the patient and answer any questions they may have about using their glucometer. 3. Reinforce/explain to the patient not to delete their glucose reading log from the glucometer because we will extract the log from the glucometer at subsequent visits. Abnormal Blood Glucose Safety Protocol: The study clinician will be notified by the way to health platform if participants glucose is either extremely low or high (60 or 400 mg/dL) and respond accordingly. The study clinician will contact these patients to address the issue. Step Seven: CHW escalation 1. The way to health platform will notify the study team of any individuals who have low adherence (no self-monitoring) or elevated glucose readings (300 mg/dL) for 30% of days over any 2 week period in the first 12 weeks of the study. These individuals will be assigned to receive ongoing CHW support for the duration of the 24-week study period 2. The study team should notify the CHW and send them the patients redcap ID. The CHW will follow up with the patient in 1-2 days. Step Eight: 3 Month Follow Up 1. One month prior, contact the patient to set a date/time for their 3 month follow up appointment. (If patients are unable to be reached, then we will send a letter to their home requesting that they contact us to set up a follow-up appointment.) 2. At the appointment, obtain the blood glucose log of readings from the patients glucometer. 3. Provide the patient with a gift card. Follow up visit is concluded. 4. The window to complete all 3-month follow-up procedures may be extended in cases where patients were prevented from completing visits within the original window due to COVID-19 restrictions. Step Nine: 6 Month Follow Up and Labs 1. One month prior, contact the patient to set a date/time for their 6 month follow up appointment. (If patients are unable to be reached, then we will send a letter to their home requesting that they contact us to set up a follow-up appointment.) 2. At the appointment, obtain the blood glucose log of readings from the patients glucometer. 3. Administer the follow up redcap survey 4. Walk the patient to the laboratory to have their blood drawn for HbA1c evaluation. 5. Provide the patient with a gift card. Follow up visit is concluded. 6. The window to complete all 6-month follow-up procedures may be extended in cases where patients were prevented from completing visits within the original window due to COVID-19 restrictions. Any Engage Study patients screened for recruitment into routine care community health worker programs at Penn Medicine will have their enrollment deferred until their study participation is complete. We will track all screened patients that are deferred because of Engage Study participation and contact them afterwards to offer enrollment into our routine care community health worker program. You may also be contacted during this study as a part of our quality review. If this happens you will just be asked a few questions about how the study has been going and your experiences with the steps listed above.

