risk of low adherence and a linear regression model to obtain the between-arm difference in change in glycosylated hemoglobin. We will adjust these models for any unbalanced baseline covariates to increase efficiency. For exploratory purposes, we will do a per protocol analysis focusing on the subgroup of patients in the hybrid intervention who actually received CHW support, as compared to the patients in the DHI alone arm who would have received support based on low adherence or elevated glucoses. We will also explore predictors of adherence and glycosylated hemoglobin across all three arms. Sample size calculations Based on a similar 24-week trial, we assume that the adherence rate in the usual care arm will be 40% and the rate in the hybrid intervention will be 80%. In the prior trial, the adherence rate in the usual care arm was 47%; however this trial had a lower risk population (higher income and lower baseline glycosylated hemoglobin), and a longer financial incentive period. In this same trial, the adherence rate for the DFI alone arm was 70%; therefore the estimate of 80% adherence in the hybrid DFI/CHW arm seems reasonable. Using a two-sample comparison of proportions (usual care versus hybrid), we will require a sample size of 28 patients per arm to detect these differences with 80% power, assuming a Type I error rate of 0.05. Given the vulnerability and transience of this patient population, it is important to account for loss to follow-up, which we assume based on prior trials to be 20%. Therefore, we estimate that we will have to enroll 34 patients in each arm to end up with our minimal sample size. Our planned enrollment of 50 patients in each arm will easily allow us to meet this threshold. Our planned sample size will also allow us to detect a difference between DFI alone and hybrid arms (the secondary outcome), assuming the DFI arm has an adherence rate of 48% and the hybrid arm has a rate of 80%. In reality, we might see higher adherence than 48% in the DFI alone arm based on a prior similar trial as above in which the DFI arm had a 70% adherence. However, it is possible in this trial focusing on a vulnerable population, DFI alone may result in lower adherence. Missing data Efforts will be made to collect complete information on patients including 3 attempts to contact each patient via telephone and the provision of honoraria for completion of follow-up. We will check the medical record of those lost to follow-up and extract from the electronic medical record any relevant glycosylated hemoglobin that occurred within 4 weeks of the study completion date. We will track all missing values and assess the pattern of missing data and whether the missingness is non-ignorable. If appropriate, we will consider statistical methods such as multiple imputation.

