CHWs and clinicians will enter data directly into REDCap, which obviates the need for transferring written data into electronic form; this significantly improves the quality of data. Penn has licensed its own version of REDCap housed on our own servers located within a University of Pennsylvania Health System (UPHS) data center inside the UPHS firewall and therefore afforded the same network protections as all UPHS sensitive clinical data. REDCap was developed specifically around HIPAA-compliant guidelines and is recommended to Penn Medicine researchers by our Office of Human Research. Relevant HIPAA-compliant features include password-protected access to the system, restriction of access to specific clinical trial data to designated users, audit trails of access and data updates, and built-in de-identification functions that can be used when exporting data for analysis. REDCap has been disseminated for use locally at other institutions and currently supports 170 academic/non-profit consortium partners on six continents and 13,000 research end-users (www.project-redcap.org). RAs and goal-supporters can access REDCap through a web-based interface and securely input data from any location at the time of data collection minimizing the need for travelling with either electronic or paper versions of sensitive information. Audio recordings of qualitative interviews will be temporarily stored on a password protected, PGP-Netshare encrypted HIPAA secure network drive behind the firewall of the Division of General Internal Medicine server. This network drive was established per the advice and recommendation of the Division of General Internal Medicines UPHS affiliated Local Support Provider within Penn Medicine Academic Computing Services. Once the audio files are uploaded to the transcription service website and the written transcripts are returned the audio recordings will be destroyed. Interview transcripts will then be uploaded to REDCap. Written communication to study participants will also be stored on this drive which is accessible only by members of the research team. A unique participant identifier will be used for linkage of Personal Health Information (PHI) to research databases. The unique study identification number, and no other identifying information, will be used on all data collection instruments. The only paper forms that will be used in this study are: 1) informed consent documents and 2) human subject vouchers for participant incentives. These paper forms will be securely stored in a locked cabinet in the School of Medicine. One exception to the utilization of paper forms is as follows: In the event that data is unable to be directly entered into REDCap for any reason (e.g. due to a technological system failure), a paper copy of the corresponding Data Collection Instrument will be utilized and the Data will then be transcribed from the paper form and entered into REDCap immediately after any technological issues are rectified. The paper form will be retained as a source document. Research material will be obtained from participant surveys and from glucometers. All participants will provide informed consent for access to these materials. Research material that is obtained will be used for research purposes only. The Penn Medicine Academic Computing Services (PMACS) will be the hub for the hardware and database infrastructure that will support the project and is where the Way to Health web portal is based. The PMACS is a joint effort of the University of Pennsylvania's Abramson Cancer Center, the Cardiovascular Institute, the Department of Pathology, and the Leonard Davis Institute. The PMACS provides a secure computing environment for a large volume of highly sensitive data, including clinical, genetic, socioeconomic, and financial information. Among the IT projects currently managed by PMACS are: (1) the capture and organization of complex, longitudinal clinical data via web and clinical applications portals from cancer patients enrolled in clinical trials; (2) the integration of genetic array databases and clinical data obtained from patients with cardiovascular disease; (3) computational biology and cytometry database management and analyses; (4) economic and health policy research using Medicare claims from over 40 million Medicare beneficiaries. PMACS requires all users of data or applications on PMACS servers to complete a PMACS-hosted cybersecurity awareness course annually, which stresses federal data security policies under data use agreements with the university. The curriculum includes Health Insurance Portability and Accountability Act (HIPAA) training and covers secure data transfer, passwords, computer security habits and knowledge of what constitutes misuse or inappropriate use of the server. We will implement multiple, redundant protective measures to guarantee the privacy and security of the participant data. All investigators and research staff with direct access to the identifiable data will be required to undergo annual responsible conduct of research, cybersecurity, and HIPAA certification in accordance with University of Pennsylvania regulations. All data for this project will be stored on the secure/firewalled servers of the PMACS Data Center, in data files that will be protected by multiple password layers. These data servers are maintained in a guarded facility behind several locked doors, with very limited physical access rights. They are also cyber-protected by extensive firewalls and multiple layers of communication encryption. Electronic access rights are carefully controlled by University of Pennsylvania system managers. We will use highly secure methods of data encryption for all transactions involving participants financial information using a level of security comparable to what is used in commercial financial transactions. We believe this multi-layer system of data security, identical to the system protecting the University of Pennsylvania

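### The exploratory per-protocol comparison selects hybrid patients on trigger plus receipt of CHW support, but DFI-alone patients on the trigger alone

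*Combined protocol and SAP*

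**What the plan says.** Under Statistical analyses, the Analysis Plan tests the hypotheses by intent-to-treat and adds an exploratory per-protocol analysis. It sets out the two groups as follows: "subgroup of patients in the hybrid intervention who actually received CHW support, as compared to the patients in the DHI alone arm who would" (DHI is evidently DFI). The DFI-alone comparators are those "who would have received support based on low adherence or elevated glucoses", which is the trigger with no condition about uptake.

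The path from trigger to support is described in two places:

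- **Procedures, Step Seven.** The platform flags patients with no self-monitoring or elevated readings on 30% of days in any 2-week period of the first 12 weeks. "These individuals will be assigned to receive ongoing CHW support for the duration of the 24-week study period". Then "The study team should notify the CHW and send them the patients redcap ID".
- **Design, Hybrid DFI/CHW Arm.** Once notified of a struggling patient, the CHW acts: "she will visit the patient at home within 1-2 days to initiate the IMPaCT intervention". This section also says of the expected number: "we estimate that 50% (25 of the 50 patients in to the hybrid intervention) will require support from a CHW".

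Before any trigger, the hybrid arm has the glucometer on the same terms and "financial incentives just as in the DFI intervention".

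**The concern.** The two groups are formed by different rules. Being flagged, being assigned, having the CHW notified and being visited at home are separate events, and a patient can be lost between any two of them. When that happens in the hybrid arm, the patient leaves the per-protocol group. The corresponding patient in the DFI-alone arm, who would also have been missed, cannot be identified and stays in. The plan does not define receipt, does not say how triggered but unsupported hybrid patients are handled, and sets no matching condition for DFI alone.

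If patients who cannot be reached or who decline support also monitor differently, randomisation no longer protects the comparison. A difference between the groups could then partly reflect who received support and not what support did. This is the planned analysis aimed at the patients escalated to a CHW, so readers are likely to look to it for the effect of CHW support.

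**Working it through.** **Figure from the plan.** The documents give no figure for this comparison. The only relevant one is the expected number escalated in the hybrid arm: 50% × 50 = 25, as stated. I assume the same number trigger in the DFI-alone arm, since terms before the trigger are the same.

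**Notation.** Among triggered patients, and supposing CHW support has no effect:

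- *u* = share of triggered hybrid patients who receive no support (not given; assumed 10%, 20%, 40%)
- *R*, *N* = mean adherence of patients who would and would not receive support (not given; assumed gap *R − N* from −10 to 20 points)

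**Bias.** The DFI-alone group contains both kinds of patient, so its mean is (1 − u)R + uN. The hybrid group contains only receivers, so its mean is R. The spurious difference is

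R − [(1 − u)R + uN] = u(R − N).

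| R − N (points) | u = 10% | u = 20% | u = 40% |
|---|---|---|---|
| 20 | +2 | +4 | +8 |
| 10 | +1 | +2 | +4 |
| 0 | 0 | 0 | 0 |
| −10 | −1 | −2 | −4 |

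A positive value favours the hybrid arm. Check: let all triggered patients average 40% (assumed), with R − N = 20 and u = 20%. Then R = 44 and N = 24, since 0.8 × 44 + 0.2 × 24 = 40, and R − 40 = 4.

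**Precision.** The 95% half-width is 1.96 × SD × √(2/n). With n = 25 per arm it is 11.1, 16.6 or 22.2 points for an assumed SD of 20, 30 or 40. With n = 20 per arm and SD 30 it is 18.6.

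**Effect on the false-positive rate (normal approximation, two-sided 5%).**

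- u = 20%, gap 20, SD 30: 20 supported against 25 triggered patients. The standard error is 30 × √(1/20 + 1/25) = 9.0, the half-width is 17.6, and the bias of 4 gives about 7%.
- u = 40%, gap 20, SD 20: 15 against 25. The standard error is 20 × √(1/15 + 1/25) = 6.5, and the bias of 8 gives about 23%.

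**Simulation.** With 25 triggered per arm, SD 20, no CHW effect and a 30-point gap (larger than in the table), the comparison as written rejected in 14.5% of runs at u = 20% and about 37% at u = 40%. With both arms selected on the trigger alone, the mean difference was 0.000 and rejection stayed near 5% in the same settings. These runs confirm the formula and the repair; they are not a forecast for this trial.

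**The case against.** The wording can be read more kindly, as actual against hypothetical escalation under one and the same trigger. The trigger leads straight to assignment with contact in 1-2 days, and the estimate of 25 of 50 makes no allowance for non-receipt. On that reading the plan already makes the like-for-like comparison and is only loosely worded. But a per-protocol label together with the stress on actual receipt points to receipt, and participants may withdraw at any time, so the two definitions can diverge.

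Several other objections stand:

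- The analysis is exploratory. No hypothesis test, including hybrid against DFI alone, and no sample-size figure depends on it.
- The bias needs two conditions, and the documents quantify neither. The Background says that non-responders in earlier CHW work disengaged and avoided self-monitoring, which suggests a direction. Those patients already had a CHW, however, so this is weak evidence about patients never supported.
- In most of the assumed range the bias is small against the noise.
- The illustration uses mean adherence. The plan's adherence model gives a relative risk of low adherence, and the outcome for the per-protocol analysis is not named, so the point figures do not carry over directly.
- Selecting on the trigger changes the question from support received to escalation as assigned.

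These limit the weight of the point. They do not make the two groups comparable as defined.

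**Conclusion.** The concern holds, as a minor point. On the natural reading, the two groups are selected by different rules, and nothing elsewhere in the documents repairs this. Neither the direction nor the size of the bias can be fixed from the documents. Over the assumed inputs it runs from −4 to +8 points of mean adherence, and it is zero if every triggered hybrid patient is supported or if receipt is unrelated to adherence.

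Selecting on the trigger alone is sound because the first trigger precedes any CHW contact and occurs under the same glucometer and lottery terms in both arms. It does assume that knowing a CHW might be assigned does not itself change early monitoring.

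**What to change.** Define both groups by the trigger alone. Compare all hybrid patients who met it in the first 12 weeks, supported or not, with all DFI-alone patients who met it under the same algorithm. Report the number of hybrid patients triggered but not supported. Keep the receipt-based comparison as a supplement, with receipt defined in advance. As an optional refinement, count adherence from the first trigger date in both arms.

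The cost is a change of wording, since the plan already has to run the trigger on DFI-alone data. Receipt may be countable because, under Subject Confidentiality, "CHWs and clinicians will enter data directly into REDCap", although the documents do not say which CHW contacts are recorded. The downside is that the estimate may be smaller once unsupported patients are included, and precision remains low.

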In the 21st century, in the most developed country in the world, a black man living in poverty in Southwest Philadelphia dies of diabetes at the age of 45. He is not unique. Low-income Americans have higher rates of almost every disease and die 15 years sooner than wealthier counterparts who live just a few blocks away. Why and what can be done? Health and health inequity are heavily influenced by personal behaviors; staying healthy requires devoting energy and resources to performing certain behaviors (exercise, diet, medication adherence, etc.) and avoiding others (smoking, alcohol, etc.). Engaging in health-promoting behavior is challenging, especially in the face of socioeconomic barriers like food insecurity or joblessness. In essence, low-income individuals run a difficult race with a severe handicap. A conceptual framework is useful for understanding the hurdles that an individual must overcome in the path to healthy behavior. Figure 1 is a framework that draws from three evidence-based models for behavior-dependent outcomes: the Reasoned Action Approach, the Health Belief Model and the Transtheoretical Model (Stages of Change). For an individual to even intend to initiate a behavior, her attitudes, social norms, and self-efficacy must all fall in line. Once an individual intends to initiate a behavior, she can be thwarted by external barriers. If she manages to initiate a behavior, she will still require reinforcement in order to turn the behavior into a habit. Fortunately, there have been two categories of interventions that show promise for promoting behavior change and improving health outcomes: digital health interventions and community health workers (CHWs). Digital health interventions use computers, mobile phones or devices to encourage self-monitoring of health metrics like blood glucose or weight. By raising an individuals awareness of their metrics and attendant health risks, digital interventions can shift attitudes to promote healthy behavior (Figure 2A). Digital interventions can be augmented by behavioral economic engagement strategies such as lottery-based financial incentives, which serve to reinforce self-monitoring behavior so that it becomes a habit (Figure 2A). Our study team has run dozens of digital and financial incentives (DFI) interventions; these have significantly increased physical activity, improved glycemic control, smoking cessation rates, and helped people lose weight. The ongoing advances in technologies related to wearable tracking devices and point of-care testing are likely to fuel increasing interest in DFI interventions. Yet, recent meta-analyses show that these approaches are limited by low uptake and high levels of attrition over time. In one of our recent studies, the rate of adherence to daily glucose self-monitoring was only 60% over a 6-month period, even with the addition of lottery-based financial incentives. Increasing success rates, particularly among vulnerable populations, will likely require additional support to address underlying socioeconomic barriers that make it hard for low-income people to manage their health in the first place. Otherwise, struggling patients may find it self-defeating to monitor elevated sugars, weight or blood pressure without the necessary supports to correct them.¹⁵ Community health workers (CHWs) are trusted laypeople from the local community who can be hired and trained by healthcare organizations to support patients. Their shared identity with low-income patients allows CHWs to influence attitudes, shift social norms, bolster self-efficacy through strategies like motivational interviewing, and address socioeconomic barriers to healthy behaviors (Figure 2B). CHW interventions are increasingly being used to improve health in disadvantaged communities and can improve chronic disease outcomes, but often are disease-specific, difficult to scale across institutions or lacking in high-quality evidence. Our study team has developed a standardized, scalable CHW intervention called

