
The following documents are currently attached to this item:

There are no documents attached for this item.

Deception

Does your project use deception? Deception could be considered any direct misinformation presented to the subject or omission of key information pertaining to the design or nature of the project.

No

International Research

Are you conducting research outside of the United States?

No

Analysis Plan

Hypotheses 1. We hypothesize that over the 24-week study period, compared to usual care, the hybrid intervention will lead to a higher rate of adherence to daily glucose self-monitoring. 2. Our secondary hypothesis is that compared to DFI alone, the hybrid intervention will lead to a higher rate of adherence to daily glucose self-monitoring. 3. Our exploratory hypotheses are that compared to usual care and DFI alone, the hybrid intervention will lead greater improvements in glycosylated hemoglobin. Outcome measures The primary and secondary outcome measures will be adherence rate (constructed by summing the number of days in the study period that the glucometer was used divided by the total number of days in study period). The exploratory outcome measure will be change in glycosylated hemoglobin from baseline to 24 weeks follow-up assessment. Statistical analyses We will test our hypotheses with an intent-to-treat analysis using a modified Poisson regression model to obtain relative

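### The sample size treats adherence rates, defined as shares of days, as proportions of patients, so its figures describe neither the defined outcome nor the planned low-adherence analysis

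*Combined protocol and SAP*

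**What the plan says.** The outcome is defined under Primary outcome variable(s) and again in the Analysis Plan under Outcome measures. The latter says "The primary and secondary outcome measures will be adherence rate", and describes it as "constructed by summing the number of days in the study period that the glucometer was used divided by the total number of days in study". That is a number between 0 and 1 for each patient.

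The sample size text in the Analysis Plan uses the same term for its inputs: "we assume that the adherence rate in the usual care arm will be 40% and the rate in the hybrid intervention will be 80" per cent. It puts these into a test of two proportions: "Using a two-sample comparison of proportions (usual care versus hybrid), we will require a sample size of 28 patients per arm". The target there is a power of 80% at alpha 0.05. It allows for 20% loss and plans 50 patients per arm. For the secondary contrast it says the planned size also suffices "assuming the DFI arm has an adherence rate of 48% and the hybrid arm has a rate of 80" per cent. It adds that DFI adherence might be higher, because a similar earlier trial saw 70%.

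Under Statistical analyses, adherence is to be analysed by modified Poisson regression for the relative risk of low adherence. No 24-week cut-off for low adherence is given, and no between-patient SD of the adherence rate appears anywhere.

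**The concern.** A two-proportion calculation treats each patient as a single yes/no result with variance p(1-p). The outcome is instead a share of about 24 weeks of days. Its arm-level summary is a mean, and its spread depends on how patients differ. The Background section uses the term in this day-share sense for an earlier study: "the rate of adherence to daily glucose self-monitoring was only 60% over a 6-month period, even with the addition of lottery-based financial incentives".

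If 40%, 80% and 48% are average shares of days, they are not the percentages of patients who meet some criterion. The calculation then answers a question that the trial does not ask. The hybrid-versus-DFI statement suffers most. That contrast isolates the community health worker component, and the 48% figure is all the plan says about what difference it can detect.

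**Working it through.** **Inputs from the plan.** Rates 0.40 (usual care), 0.48 (DFI) and 0.80 (hybrid); alpha 0.05, taken as two-sided because that reproduces the plan's figure; power 80%; 50 per arm with 20% loss, so 50 × 0.80 = 40 evaluable.

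**Inputs assumed.** Between-patient SD of the share 0.20 to 0.40. The ceiling for arms with means 0.40 and 0.80 is √((0.24 + 0.16)/2) ≈ 0.447, reached only if every patient tests on all days or on none.

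**1. Reproducing the plan.** With p̄ the average of the two rates and d their difference:

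n = [1.96√(2p̄(1−p̄)) + 0.842√(p₁(1−p₁) + p₂(1−p₂))]² / d²

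Continuity-corrected: n′ = (n/4)[1 + √(1 + 4/(nd))]²

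- 40% vs 80%: n = (1.358 + 0.532)² / 0.16 = 22.3; n′ = 27.1, which rounds up to the printed 28.
- 48% vs 80%: n = (1.330 + 0.539)² / 0.1024 = 34.1; n′ = 40.1, almost exactly the 40 evaluable. Corrected power at 40 per arm is about 80%.

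Both statements therefore match a calculation in which each patient is one yes/no observation.

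**2. If mean shares are compared (the outcome as defined).** Two-sample t-test, noncentral t with 2n − 2 degrees of freedom and noncentrality d / (SD√(2/n)). Example: SD 0.35, n = 28, d = 0.40 gives 0.40 / 0.0935 = 4.28 and power 98.7%. The detectable difference at 40 per arm is close to (1.96 + 0.842) × SD × √(2/40) = 0.627 × SD. The t-based values below are slightly larger and are rounded up to the next half point.

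| SD | Power, 40% vs 80%, 28 per arm | Detectable gap at 80% power, 40 per arm | Power, 70% vs 80%, 40 per arm |
|---|---|---|---|
| 0.20 | >99% | 13 points | 60% |
| 0.25 | >99% | 16 points | 42% |
| 0.30 | 99.8% | 19.5 points | 31% |
| 0.35 | 98.7% | 22.5 points | 24% |
| 0.40 | 96% | 25.5 points | 20% |

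The plan's statement corresponds to 80 − 48 = 32 points.

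**3. If low adherence is tested (the analysis as named).** The inputs must be proportions of patients below a cut-off. To see what the stated means imply, assume beta-distributed shares with mean m and SD s, so k = m(1−m)/s² − 1 and the parameters are mk and (1−m)k. Take SD 0.20 to 0.35 and use the uncorrected two-proportion power formula. Example: SD 0.30 and a cut-off at 20% of days put 23.8% of DFI patients and 8.7% of hybrid patients below it, and power at 40 per arm is about 45%.

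| Cut-off (share of days) | Power, 48% vs 80%, 40 per arm | Power, 40% vs 80%, 40 per arm |
|---|---|---|
| 20% | 36-45% | 75-81% |
| 50% | 88% or more | 98% or more |

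**4. The plan's method at 70% vs 80%.** The uncorrected two-proportion formula at 40 per arm gives about 18% power, close to the bottom of the 20-60% range in step 2.

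**The case against.** The case for leaving the text alone has four parts.

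- **The calculation is correct for its inputs.** This stands. A reader might infer that 28 is a miscalculation, but it reproduces exactly. The fault lies in what the inputs measure.
- **A two-proportion test suits the modified Poisson analysis of a patient-level yes/no.** The form does match, and this stands as far as it goes. For the calculation to apply, though, 40%, 80% and 48% would have to be proportions of patients on one side of a cut-off, and the plan gives none. The rule that triggers community health worker support (30% of days over any 2-week period in the first 12 weeks) governs escalation and does not define a 24-week outcome.
- **The mistake is on the safe side.** This stands for a comparison of means, because a share between 0 and 1 cannot vary more than a yes/no result with the same mean. It does not carry over to low adherence, where power can fall well below 80%.
- **Restating the figures may not change how a null result is read.** This stands in part. At the earlier trial's 70% for DFI against 80%, power is low by either method, so a null there is uninformative anyway. The confidence interval will matter more than any planned figure.

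The SD range is an assumption. The plan also never says outright that 40%, 80% and 48% are means of day-shares. That reading follows from its own definition of the term and its use in the Background.

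**Conclusion.** The point holds as a mismatch between the sizing and the endpoint. The 28 per arm, the 80% power and the 48%-versus-80% statement belong to a patient-level proportion that the plan does not define.

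The size of the error depends on which analysis is meant. For mean shares the sizing is conservative. For low adherence it may be too optimistic or too pessimistic, depending on the missing cut-off. These results rest on the assumed SDs and, for low adherence, on the beta shape.

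Two stronger readings are tempting, and the documents support neither. One is that the trial is underpowered: for 40% versus 80% on mean shares, 50 per arm is ample, and on low adherence nothing can be said without a cut-off. The other is that a null hybrid-versus-DFI result would be good evidence against a moderate community health worker benefit: the plan's own 70% figure for DFI leaves a 10-point gap, below every detectable difference in the first table.

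**What to change.** Keep 50 per arm. State one primary analysis of adherence and size that one:

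- **Preferred:** a comparison of mean day-share, which is the outcome as defined, with a justified between-patient SD. Take the SD from the earlier trial if it is available; otherwise state a range. The documents do not say whether the study team has access to it.
- **Alternative:** low adherence, with a stated 24-week cut-off and the expected proportion of patients below it in each arm.

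On the chosen scale, restate the power for usual care versus hybrid at 40 evaluable per arm. Replace the 48% statement with the smallest hybrid-versus-DFI difference detectable with 80% power at 40 evaluable per arm.

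The cost is one recalculation and a wording change, with no effect on enrolment, visits or data collection. The downside is that the new figures rest on an SD or cut-off that has to be justified.
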